7.1 DEMOGRAPHIC AND OTHER BASELINE CHARACTERISTICS

Only descriptive statistics are planned for this section of the report, based on the TS.

The data will be summarised in total.

7.2 CONCOMITANT DISEASES AND MEDICATION

Frequency tables are planned for this section of the report, based on the TS.

Concomitant diseases will be coded using the coding system of the Medical Dictionary for Drug Regulatory Activities (MedDRA). Medications will be coded using the World Health Organization Drug Dictionary (WHO-DD). The coding version number will be displayed as a footnote in the respective output.

The diagnoses and medications will be listed. Subjects without any concomitant diagnoses or concomitant therapies should be marked with a “No” in the respective column.

The relevance of the concomitant therapies to the evaluation of PK will be decided no later than at the RPM/DBLM.

7.3 TREATMENT COMPLIANCE

Section 4.3 of the CTP: *Compliance will be assured by administration of all trial medication in the study centre under supervision of the investigating physician or a designee. The measured plasma concentrations of trial medication will provide additional confirmation of compliance.*

It is not intended to list the compliance separately. Any deviations from complete intake will be addressed in the RPM/DBLM (cf. TSAP [Section 6.2](#)) and described in the CTR.

7.4 PRIMARY ENDPOINTS

Primary analysis

Relative bioavailability is to be determined on the basis of the primary PK endpoints (AUC_{0-tz} , C_{max}). Those parameters will be ln-transformed (natural logarithm) prior to fitting the ANOVA model (see below).

Section 7.3.1 of the CTP: *The statistical model used for the analysis of the primary endpoints will be an analysis of variance (ANOVA) model on the logarithmic scale. That is, the PK endpoints will be log-transformed (natural logarithm) prior to fitting the ANOVA model. This model will include effects accounting for the following sources of variation: subjects and treatment. The effect ‘subjects’ will be considered as random, whereas ‘treatment’ will be considered as fixed. The model is described by the following equation:*

$y_{km} = \mu + s_m + \tau_k + e_{km}$, where

y_{km} = logarithm of response measured on subject m receiving treatment k ,

μ = the overall mean,

s_m = the effect associated with the m^{th} subject, $m = 1, 2, \dots, n$

τ_k = the k^{th} treatment effect, $k = 1, 2,$

e_{km} = the random error associated with the m^{th} subject who received treatment k .

The difference between the expected means for test treatments and reference treatment $\ln(T) - \ln(R)$, estimated by the difference in the corresponding Least Square Means (point estimate) and two-sided 90% confidence intervals based on the t-distribution, will be computed. These quantities will then be back-transformed to the original scale to give the point estimator (geometric mean) and interval estimates for the ratio between response under test and response under reference.

The implementation for this analysis will be accomplished by using the XPKISTAT macro, based on PKS, and option BWU (Bioavailability/Bioequivalence, within-subject design, uncontrolled w.r.t. time).

Further analysis

Section 7.3.1 of the CTP: *The same statistical model as stated above will be repeated for the primary endpoints but with 'subject' considered as fixed effects.*

The following SAS code can be used to fit the model:

```
PROC GLM DATA=indata;
  CLASS subject treatment;
  MODEL logkp = treatment subject;
  LSMEANS treatment / PDIFF=CONTROL("Ref_trt") CL ALPHA=0.1;
  RUN;
```

Further analysis of primary endpoints is explorative.

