2.1.2 Primary endpoints

The following pharmacokinetic parameters will be determined for BI 730357:

- AUC_{0-tz} (area under the concentration-time curve of the analyte in plasma over the time interval from 0 to the last quantifiable data point)
- C_{max} (maximum measured concentration of the analyte in plasma)

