7. STATISTICAL METHODS AND DETERMINATION OF SAMPLE SIZE

7.1 STATISTICAL DESIGN – MODEL

The main objective of this trial is to investigate the relative bioavailability of BI 730357 in plasma when given as oral single dose together with multiple oral doses of itraconazole (Test, T) as compared to when given alone as oral single dose (Reference, R) on the basis of the primary and secondary pharmacokinetic endpoints, as listed in Section [2.1.2](#) and [2.1.3](#). The trial is designed to allow intra-subject comparisons and will be evaluated statistically by use of a linear model for logarithmically transformed PK endpoints.

A further objective is to evaluate and compare further pharmacokinetic parameters between the treatments, see Section [2.2.1](#). These further pharmacokinetic parameters will be assessed by descriptive statistics.

The assessment of safety and tolerability is a further objective of this trial, and will be evaluated by descriptive statistics for the parameters specified in Section [2.2.2.2](#).

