7.2 NULL AND ALTERNATIVE HYPOTHESES

The relative bioavailability of BI 730357 in plasma after test versus reference treatment will be estimated by the ratios of the geometric means (test/reference), and their corresponding 2-sided 90% confidence intervals (CIs) will be provided. This method corresponds to the two one-sided t-tests procedure, each at the 5% significance level. Since the main focus is on estimation and not testing, a formal hypothesis test and associated acceptance range is not specified.

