7.3 PLANNED ANALYSES

Analysis sets

Statistical analyses will be based on the following analysis sets:

- Treated set (TS): The treated set includes all subjects who were entered and treated with at least one dose of study drug. The treated set will be used for safety analyses.
- Pharmacokinetic parameter analysis set (PKS): This set includes all subjects in the treated set (TS) who provide at least one PK endpoint that was defined as primary or secondary and was not excluded due to a protocol deviation relevant to the evaluation of PK or due to PK non-evaluability (as specified in the following subsection ‘Pharmacokinetics’). Thus, a subject will be included in the PKS, even if he contributes only one PK parameter value for one period to the statistical assessment. Descriptive and model based analyses of PK parameters will be based on the PKS.

Adherence to the protocol will be assessed by the trial team. Important protocol deviation (IPD) categories will be suggested in the IQRM plan, IPDs will be identified no later than in the Report Planning Meeting, and the IPD categories will be updated as needed.

Pharmacokinetics

The pharmacokinetic parameters listed in Section [2.1](#) for drug BI 730357 will be calculated by means of non-compartmental analysis. Noncompartmental pharmacokinetic parameters will be calculated based on actual sampling times using a validated pharmacokinetic software (Phoenix® WinNonlin® 6.3). Descriptive statistics will be used to evaluate plasma concentration data and PK parameters. The derivation of PK parameters is described in BI internal SOP ([001-MCS-36-472_RD-01](#)). Further details on analysis will be described in the TSAP.

Plasma concentration data and parameters of a subject will be included in the statistical pharmacokinetic (PK) analyses if they are not flagged for exclusion due to a protocol deviation relevant to the evaluation of PK (to be decided no later than in the Report Planning Meeting) or due to PK non-evaluability (as revealed during data analysis, based on the criteria specified below). Exclusion of a subject's data will be documented in the CTR.

Relevant protocol deviations may be

- Incorrect trial medication taken, i.e. the subject received at least one dose of trial medication the subject was not assigned to
- Incorrect dose of trial medication taken
- Use of restricted medications

Plasma concentrations and/or parameters of a subject will be considered as non-evaluable, if for example

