4. CHANGES IN THE PLANNED ANALYSIS OF THE STUDY

All analyses as planned in the CTP will be performed and are described in more detail in this TSAP.

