The ADS ADPP (PK parameters) contains column variables indicating inclusion/exclusion (APEXC) of a PK parameter and an analysis flag comment (APEXCO). All analyses based on the PKS will include parameters if they are not flagged for exclusion, that is APEXCO is equal to "Included".

Exclusion of PK concentrations

The ADS ADPC (PK concentrations per time-point or per time-interval) contains column variables ACEXC or ACEXCO indicating inclusion/exclusion (ACEXC) of a concentration and an analysis flag comment (ACEXCO). Exclusion of a concentration depends on the analysis flag comment ACEXCO. For example, if ACEXCO is set to 'ALL CALC', the value will be excluded for all types of analyses based on concentrations. If ACEXCO is set to 'DESC STATS', the value will be excluded from descriptive evaluations per planned time point/time interval. If ACEXCO contains the addition 'TIME VIOLATION' or 'TIME DEVIATION', the value can be used for further analyses based on actual times. If ACEXCO is set to 'HALF LIFE', the value will be excluded from half-life calculation (and, as a consequence, any calculation that relies on λ_z) only; the value is included for all other analyses.

Further details are given in 001-MCS-36-472_RD-01 "Noncompartmental Pharmacokinetic / Pharmacodynamic Analyses of Clinical Studies" ([5](#)) and 001-MCS-36-472_RD-03 "Description of Analytical Transfer Files and PK/PD Data Files" ([7](#)).

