7.5.2 Secondary endpoints

The secondary PK endpoint $AUC_{0-\infty}$ will be assessed using the same methods as described for the primary endpoints but will not be interpreted in a confirmatory sense.

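### Must the plan say how to read AUC0-tz and AUC0-∞ together if itraconazole strongly prolongs the half-life of BI 730357?

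*SAP*

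**What the plan says.** Protocol 2.1.2 makes AUC0-tz (the area "over the time interval from 0 to the last quantifiable data point") and Cmax primary. Protocol 2.1.3 makes AUC0-∞ secondary. The SAP repeats both in Sections 5.1 and 5.2.2.

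The two documents describe the basis for relative bioavailability differently:

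- Protocol 7.1 assesses the main objective "on the basis of the primary and secondary pharmacokinetic endpoints". The synopsis also covers both classes of endpoint.
- SAP 7.4 says "Relative bioavailability is to be determined on the basis of the primary PK endpoints".
- SAP 7.5.2 says AUC0-∞ "will be assessed using the same methods as described for the primary endpoints but will not be interpreted in a confirmatory sense".
- SAP 4 declares no change: "All analyses as planned in the CTP will be performed and are described in more detail in this TSAP".

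Protocol 7.2 sets no test or acceptance range for any endpoint: "Since the main focus is on estimation and not testing". Protocol 7.3 takes the derivation of PK parameters from an internal procedure and adds that "Further details on analysis will be described in the TSAP". SAP 7 refers to the same procedure. It also describes a flag for single concentrations under which "the value will be excluded from half-life calculation", together with anything else that relies on the terminal slope.

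**The concern.** Protocol 1.4.3.3 expects higher concentrations and a longer half-life under itraconazole, and cites another drug whose AUC rose 11-fold. The Flow Chart samples the reference period (R) to 167 h and the test period (T) to 263 h. If the half-life under T becomes very long, AUC0-tz loses part of the T tail. AUC0-∞ then depends on extrapolation from late samples that span the last itraconazole dose at 191 h, after which inhibition fades.

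The two AUC ratios could then differ clearly. Protocol 7.1 seems to give both a role, SAP 7.4 seems to rest on one, and calling AUC0-∞ non-confirmatory does not separate endpoints in a trial that confirms nothing. The visible text sets no limit on the extrapolated fraction and does not say which samples define the slope. Protocol 1.4.4 says the result will inform co-medication restrictions, so one might fear that the headline AUC ratio would be picked after both are seen.

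**Working it through.** **1. The plan's own precision.** Inputs from Protocol 7.7 are n = 12, gCV 22% (AUC0-tz) or 26% (Cmax), a 90% interval and 95% tolerance probability.

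Precision = exp[ t(0.95; 11) × s × √(2/12) × √(χ²(0.95; 11)/11) ], with s = √ln(1 + gCV²).

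At 22%, s = 0.2174, so exp(1.796 × 0.2174 × 0.4082 × √(19.675/11)) = 1.2376. At 26% the result is 1.2850. The stated 1.238 and 1.285 reproduce.

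**2. Assumed model.** The half-life of BI 730357 alone and the assay limit are not in the public text. Assumptions:

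- One compartment, oral absorption rate 0.7/h, every sample quantifiable.
- R half-life 15, 20, 30 or 40 h.
- Relative clearance (1 − f) + f/(1 + I), with f = 0.9. The protocol gives about 90% of metabolism, in vitro, which is not the same as 90% of clearance.
- I constant to 191 h, then falling with a 40 h half-life (the itraconazole half-life in Protocol 1.2.2).
- AUC0-tz taken to 167 h (R) and 263 h (T).
- AUC0-∞ from a log-linear slope on the last three samples: 71, 119 and 167 h for R; 167, 215 and 263 h for T. The plan does not state this slope window.

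The yardstick is the area actually produced, integrated over the whole tail.

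**3. Sustained 5-fold effect.**

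| R half-life (h) | 15 | 20 | 30 | 40 |
|---|---|---|---|---|
| AUC0-tz ratio | 4.53 | 4.17 | 3.57 | 3.14 |
| Area actually produced, ratio | 4.67 | 4.41 | 3.94 | 3.56 |
| AUC0-∞ ratio | 4.80 | 4.69 | 4.51 | 4.40 |
| Error of AUC0-tz | −2.9% | −5.4% | −9.5% | −11.7% |
| Error of AUC0-∞ | +2.8% | +6.2% | +14.5% | +23.6% |
| AUC0-∞ above AUC0-tz | 6% | 12% | 27% | 40% |
| AUC0-tz × 1.238 | 5.61 | 5.16 | 4.41 | 3.89 |

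AUC0-tz is level with AUC0-∞ at 15 h and closer in the other three columns. The last row exceeds the produced ratio in all four.

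**4. Smaller effects.** At 3-fold the two ratios differ by 1, 3, 7 and 12%. At 2-fold they differ by at most 2%. With no effect and a 40 h half-life, the unequal schedule alone gives an AUC0-tz ratio of 1.05. The two ratios cross near 263/167 = 1.6-fold, so that figure does not mark where a problem begins.

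**5. Sensitivity to the slope.** At 5-fold and 30 h, the AUC0-∞ ratio is 4.51 from 167–263 h, 4.61 from 119–263 h, and 5.00 from 71–167 h extrapolated from 167 h.

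**6. The text side by side.** The sentence in SAP 7.4 opens the section on primary endpoints, so it names those endpoints. Section 7.5.2 then gives AUC0-∞ the same treatment. Every analysis in the protocol is still run, so the statement in SAP 4 is accurate.

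**The case for a change.** The strongest opposing case is that a strong interaction is what the protocol prepares for, and there the gap between the two reported ratios can exceed the trial's own precision: 27% and 40% at 5-fold with 30 and 40 h, against 23.8%. If the target is the ratio under continued inhibition (5 in the model) instead of the area produced in this trial, AUC0-∞ is the closer measure, and AUC0-tz × 1.238 falls short at 30 and 40 h (4.41 and 3.89).

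More extreme settings go further. In a variant with absorption rate 1/h and inhibition constant to 215 h, an 11-fold effect at a 34 h half-life gives 4.37 for AUC0-tz, 9.47 for AUC0-∞ and 5.51 produced. There 4.37 × 1.238 = 5.41 falls just short even of the produced ratio, while AUC0-∞ overshoots it by 72%. A few SAP sentences would cost little.

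What stands is that the wording differs and no visible sentence covers disagreement. It does not follow that the headline is open to choice, because AUC0-tz is ranked first in both documents and both ratios are reported with intervals. Adding weight to AUC0-∞ would, against the area produced, favour the more biased figure in the 5-fold cases at 20 h and above. Limits such as 10% disagreement or 20% extrapolation would be preference, since nothing in the documents fixes them. Slope selection and extrapolation limits may be in the cited procedure. The clinical PK text and Protocol Section 2.2.1 are not public, so their absence here does not show that the plan lacks them.

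**Conclusion.** No change is needed. Followed as written, the plan gives both AUC ratios from the same model with 90% intervals, AUC0-tz first, in an exploratory trial with no acceptance range. The difference between Protocol 7.1 and SAP 7.4 is one of wording, and aligning it would alter no result.

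The two ratios would part by more than 1.238 only with a very large effect and a long half-life: among the 2-, 3- and 5-fold cases, only at 5-fold with 30 h or more. In all the 5-fold cases the shortfall of AUC0-tz against the area produced (2.9 to 11.7%) stays inside the planned precision.

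This rests on the assumed R half-life, effect size, CYP3A share, slope window and full quantifiability, and on the area produced as yardstick. If a large gap appeared, a pharmacokineticist would see it in the two reported ratios, check the extrapolated fraction and slope, and discuss both. That is ordinary reporting and does not depend on a new rule.

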7.5 SECONDARY ENDPOINTS

7.5.1 Key secondary endpoints

This section is not applicable as no key secondary endpoints have been specified in the protocol.

7.5.2 Secondary endpoints

The secondary PK endpoint $AUC_{0-\infty}$ will be assessed using the same methods as described for the primary endpoints but will not be interpreted in a confirmatory sense.

7.7 EXTENT OF EXPOSURE

Descriptive statistics are planned for this section of the report based on the TS. The date and time of drug administration will be listed for each subject.

7.8 SAFETY ANALYSIS

All safety analyses will be performed on the TS.

The safety data for treated subjects who failed to complete the study (dropouts or withdrawals) will be reported as far as their data are available. All withdrawals will be documented and the reason for withdrawal recorded.

7.8.1 Adverse events

AEs will be coded with the most recent version of MedDRA.

The analyses of AEs will be descriptive in nature and will be based on BI standards as presented in the corporate guideline: “Analysis and Presentation of Adverse Event Data from Clinical Trials” [001-MCG-156] ([9](#)).

The standard AE analyses will be based on the number of subjects with AEs (and not on the number of AEs).

For analysis, multiple AE occurrence data on the CRF will be collapsed into an AE provided that all of the following applies:

- All AE attributes are identical (lower level term (LLT), intensity, action taken, therapy required, seriousness, reason for seriousness, relationship, outcome, AE of special interest)
- The occurrences were time-overlapping or time-adjacent (time-adjacency of two occurrences is given if the second occurrence started within one hour after end of the first occurrence)

For further details on summarization of AE data, please refer to [001-MCG-156] ([9](#)).

Section 5.2.6.1.4 of the CTP: *The following are considered as AESIs:*

- Hepatic injury
A hepatic injury is defined by the following alterations of hepatic laboratory parameters:
 - *An elevation of AST (aspartate transaminase) and/ or ALT (alanine transaminase) ≥ 3 -fold ULN combined with an elevation of total bilirubin ≥ 2 -fold ULN measured in the same blood sample, and/or*
 - *Aminotransferase (ALT, and/ or AST) elevations ≥ 10 fold ULN*
- Severe infections (grading according to *Rheumatology Common Toxicity Criteria (RCTC) developed by OMERACT [R13-3515]* ([12](#)))
- Opportunistic and mycobacterium tuberculosis infections
These include pneumocystis jirovecii, BK virus disease including polyomavirus-associated nephropathy, cytomegalovirus, posttransplant lymphoproliferative disorder (Epstein-Barr virus), progressive multifocal leukoencephalopathy, bartonellosis (disseminated only), blastomycosis, toxoplasmosis, coccidioidomycosis, histoplasmosis, aspergillosis (invasive only), candidiasis (invasive or pharyngeal), cryptococcosis, other invasive fungi (mucormycosis (zygomycosis, rhizopus, mucor, lichtheimia), scedosporium/pseudallescheria boydii, fusarium), legionellosis, listeria monocytogenes (invasive only), tuberculosis, nocardiosis, non-tuberculous mycobacterium, salmonellosis (invasive only), hepatitis B virus reactivation, herpes simplex (invasive only), herpes zoster, strongyloides (hyperinfection syndrome and disseminated forms only), paracoccidioides, penicillium marneffei, sporothrix schenckii, cryptosporidium species (chronic only), microsporidiosis, leishmaniasis (visceral only), trypanosoma cruzi Infection (Chagas' disease) (disseminated only), campylobacteriosis (invasive only), shigellosis (invasive only), vibriosis (invasive due to vibrio vulnificus), hepatitis C virus progression.

The analysis of adverse events will be based on the concept of treatment emergent adverse events.

Section 1.2.3 of the CTP: *The Residual Effect Period (REP, i.e., the period after the last dose with measurable drug levels and/or pharmacodynamic effects still likely to be present) of BI 730357 is 7 days for the mono-therapy (Treatment R). When given together with itraconazole (Treatment T), it is expected that plasma exposure of BI 730357 could be increased (albeit within the range explored in the clinical trial 1407-0001), and the time of*

relevant plasma exposure could be prolonged, which in turn could result in a prolonged period in which adverse effects could potentially occur.

For the use of itraconazole in Treatment T, the REP is defined as 9 days after last administration of itraconazole on Day 9 in Period 2. Therefore, the follow-up period will start earliest on Day 18 following BI 730357 dosing in Period 2, as this is expected to cover the period in which any potential adverse effects could reasonably occur.

According to ICH E3 ([10](#)), AEs classified as ‘other significant’ needs to be reported and will include those non-serious and non-significant adverse events with

- (i) ‘action taken = discontinuation’ or ‘action taken = reduced’, or
- (ii) marked haematological and other lab abnormalities or lead to significant concomitant therapy as identified by the Clinical Trial Leader/Investigator at the Report Planning Meeting.

An overall summary of AEs (including AESIs) will be presented.

The frequency of subjects with AEs will be summarized by treatment, primary system organ class (SOC) and preferred term (PT). Separate tables will be provided for subjects with other significant AEs according to ICH E3 ([10](#)), for subjects with serious AEs, for subjects with drug-related AEs, for subjects with drug related serious adverse events and for subjects with AESIs.

The SOC and PTs will be sorted by frequency (within system organ class). The MedDRA version number will be displayed as a footnote in the respective output.

In addition, frequencies of subjects with non-serious AEs that had an incidence of > 5% for at least one treatment will be summarised by treatment, primary SOC and PT.

For disclosure of adverse events on EudraCT additional information not included in a standard AE analysis will be performed. The following three entries will be created:

- Adverse Events per arm for disclosure on EudraCT
- Non-serious Adverse Events for disclosure on EudraCT
- Serious Adverse Events for disclosure on EudraCT

7.8.2 Laboratory data

The analyses of laboratory data will be descriptive in nature and will be based on BI standards [001-MCG-157] ([11](#)).

Laboratory data will be analysed qualitatively via comparison of laboratory data to their reference ranges. Values outside the reference range as well as values defined as possible clinically significant will be highlighted in the data listings.

It is the investigator's responsibility to decide whether a lab value is clinically significant abnormal or not (at the RPM/DBLM at the latest).

